HUMIRA® for Subcutaneous Injection Protocol for Special investigation on Long-Term administration Ulcerative Colitis

AbbVie GK

1. Purpose of Surveillance

The following were investigated in the Special investigation on Long-Term administration of "HUMIRA® for Subcutaneous Injection (Nonproprietary name: Adalimumab (Genetical Recombination)" in patients with ulcerative colitis.

- 1. Unknown adverse drug reactions (ADRs) (especially important ADRs)
- 2. Incidence and conditions of occurrence of adverse reactions in the clinical setting
- 3. Factors that may affect the safety and efficacy of Humira
- < Priority items of investigation >

Infection, tuberculosis, malignant tumor, injection site reaction, autoimmune disease, pancytopenia, demyelinating disorders, congestive cardiac failure, and interstitial pneumonia For enteral infection, the cause (virus or bacteria) will be examined.

2. Sample Size

The number of patients to be included: 1500

They are patients with ulcerative colitis who use this drug after approval.

- < Rationale for setting >
- 1. Since this survey will be conducted in actual clinical practice, the proportion of patients who have been treated with anti-TNF α products is anticipated to be high. First, considering that a dropout rate may be higher than that in Japanese clinical studies due to the enrollment of such patients, the planned sample size was calculated by assuming a dropout rate at Week 52 of 70%. Next, in the all-case survey in patients with Crohn's disease, the CDAI, an efficacy endpoint, was not recorded for approximately 30% of all the patients. Thus, by assuming the proportion of patients without assessment of Mayo score of 30%, a remission rate of 30% and the accuracy of 95% confidence interval estimation of \pm 5%, the sample size was determined to be 1500 patients (Table 1).

Table 1 Sample size calculated based on the dropout rate and accuracy

Dropout rate 70%					
Sample size	Sample size at Week 52	No. of patients assessed for Mayo score	Remission rate 30% at Week 52 95%CI	Accuracy	
500	150	105	21.2~38.8	±8.8%	
1000	300	210	23.8~36.2	±6.2%	
1500	450	315	24.9~35.1	±5.1%	
2000	600	420	25.6~34.4	±4.4%	

No. of patients assessed for Mayo score is calculated 70% of sample size at Week 52.

2. Next, for the presence or absence of history of use of anti-TNFα products, the accuracy of the remission rate used for setting the above sample size of 1500 patients was evaluated (Table 2). The following conditions were specified for the evaluation:

In data from the all-case survey of Humira in patients with Crohn's disease, 80% and 20% of the patients had used and had not used anti-TNF α products. Immediately after the drug was approved for Crohn's disease, because there were many patients waiting for the drug such as non-responders to anti-TNF α products in previous treatment, patients are likely to be enrolled in the present survey at the same ratio. Therefore, the rate for the use of anti-TNF α products in the survey was selected to be 80% and 20% for patients have used and have not used them.

The remission rate based on the Mayo score at Week 52 was set to 10% for patients who have used anti-TNF α products based on data from an overseas clinical study (M06-827) and 30% for patients who have not used them which was utilized for calculating the above sample size of 1500 patients.

Table2 Remission rate of history of anti-TNFα products use

	No. of patients	Remission		
	assessed for	rate at	95%CI	Accuracy
	Mayo score	Week 52		
History of anti-TNFα products	252	10%	6.1~13.9	±3.8%
use	232	10%	0.17~13.9	±3.8%
Without history of use of anti-	62	200/	17.9~42.1	±12.1%
TNFα products	63	30%	17.9° ~42.1	±12.1%

Based on these results, while the accuracy is poor because the number of patients in the group without history of use of anti-TNF α products is small, the data from the group with a history of use of anti-TNF α products is assumed to be an assessable numerical value (Table 2).

In a domestic clinical study of this drug in patients with ulcerative colitis (Study M10-447: 52 weeks), adverse events occurred in one patient where the incidence rate was 0.6% (1/177). On the basis of this incidence, when 1500 patients are accumulated, the 95% confidence interval for the incidence would be 0.3 to 1.1% and assessable. Even if the incidence of tuberculosis is 2%, which is higher than that in the clinical study, in this survey, by accumulating 1500 patients, the upper and lower limit of the confidence interval would be 2.84 and 1.35, respectively. Hence, because the incidence of tuberculosis (as an adverse event) shown in the Japanese clinical study in patients with rheumatoid arthritis is higher than 1.0%, it is evaluable.

In the above mentioned, we set sample size of 1500 patients in order to verify the result of

both safety and effectiveness in the clinical study.

3. Patients to Be Surveyed

Patients with moderate to severe active ulcerative colitis (only when ineffectively treated with the existing medications) who use this drug are surveyed.

< Precautions related to the indications >

This drug should be administered only to patients who present with the definite disease-related clinical symptoms even after preceding treatments with immunomodulatory agents (such as azathioprine and 6-mercaptopurine).

4. Number of Survey Centers by Clinical Practice

At least 250 centers which are department of digestive organs or likes.

< Rationale for setting >

This surveillance is carried out centering on departments specialized in digestive organs. Assuming 6 patients per center on average, more than 250 centers are required for the patients to participate in the surveillance in consideration of the feasibility.

5. Survey Centers Involved

Study centers or departments using this drug in this indication.

6. Survey Methods

(1) Surveillance system

Patients are subjected to centralized enrollment, and administered this drug at the contracted centers or departments.

- (2) Request and contract of post-marketing surveillance
 - 1) MR provides a full set of materials of information on safety measures for HUMIRA® to physicians in charge of surveillance, and explains the character of this drug, the objective of surveillance, patients to be surveyed, and survey methods.
 - 2) After the surveillance was accepted by the physician in charge, MR asks the center or department for implementation of post-marketing surveillance and contracts in writing.
- (3) Survey methods
 - 1) Paper-based CRF (case report form) is used to collect the survey data.
 - 2) Patients are observed for a period of 52 weeks after administration of this drug was initiated.
 - 3) A physician in charge of surveillance explains proper use information on this drug to participating patients, to obtain their written informed consent to participate in the surveillance.
 - 4) A physician in charge completes the enrollment form as soon as this drug was decided to be administered to the patients who consented to participation, and sends it to the

enrollment center.

- 5) A physician in charge completes CRF with the observation results at week 52 after initiation of administration, and submits the CRF to MR. In cases of the observation period uncompleted, CRF is completed promptly when the surveillance was discontinued, and submitted to MR.
- 6) MR who asked the surveillance checks enrollment form and CRF, and rechecks them as needed.

(4) Adverse Event Reporting

In the event of a serious adverse event, and additionally, any non-serious events of malignancy in patients 30 years of age and younger, whether related to adalimumab or not, if applicable - the physician will notify the AbbVie contact person (Medical Representative in Japan) within 24 hours of the physician becoming aware of the event.

(5) Product Quality Complaints

A Complaint is any written, electronic, or oral communication that alleges deficiencies related to the physical characteristics, identity, quality, purity, potency, durability, reliability, safety, effectiveness, or performance of a product/device after it is released for distribution. The investigational product in this trial contains both:

- -Biologic compound(s) and
- -Device component(s) (pre-filled syringe, pen).
- Definition

A Product Complaint is any Complaint related to the biologic or drug component of the product or to the medical device component(s).

For a product this may include, but is not limited to, damaged/broken product or packaging, product appearance whose color/markings do not match the labeling, labeling discrepancies/inadequacies in the labeling/instructions (example: printing illegible), missing components/product, device not working properly, or packaging issues.

For medical devices, a product complaint also includes all deaths of a patient using the device, any illness, injury, or adverse event in the proximity of the device, an adverse event that could be a result of using the device, any event needing medical or surgical intervention including hospitalization while using the device and use errors.

Any information available to help in the determination of causality by the device to the events outlined directly above should be captured.

Reporting

Product Complaints concerning the investigational product and/or device must be reported to the Sponsor within 24 hours of the study site's knowledge of the event via local Product Complaint reporting practices. Product Complaints occurring during the study will be followed-up to a satisfactory conclusion. All follow-up information is to be reported to the Sponsor (or an authorized representative) and documented in source as required by the

Sponsor. Product Complaints associated with adverse events will be reported in the study summary. All other complaints will be monitored on an ongoing basis.

Product complaints involving a non-Sponsor investigational product and/or device should be reported to the identified contact or manufacturer, as necessary per local regulations.

Product Complaints may require return of the product with the alleged complaint condition (syringe, pen, etc.). In instances where a return is requested, every effort should be made by the investigator to return the product within 30 days. If returns cannot be accommodated within 30 days, the site will need to provide justification and an estimated date of return.

The description of the complaint is important for AbbVie in order to enable AbbVie to investigate and determine if any corrective actions are required.

7. Surveillance Schedule

Surveillance period: July 2013 to March 2018 Enrollment period: July 2013 to July 2016

If the number of enrolled patients reached the planned sample size of the survey, the enrollment period and survey period will be reduced.

<Milestones>

Major study milestones and their planned dates are as follows:

Start of Data Collection: July 2013 Registration in the EU PAS register: Not Applicable

End of Study: The date on which statistical analysis dataset for

Clinical Study Report becomes available

Final Report of Study Result: 15 Aug 2018

8. Survey Items

(1) Observation period

Patients are observed for a period of 52 weeks after administration of this drug was started (even though the treatment is continued even after 52nd week, the CRF should be completed at the time point of week 52). When the patient is no longer followed up because of move to other hospital during the observation period, it is handled as a discontinued case.

(2) Enrollment form

Name of center, enrollment date, name of department, name of physician in charge, identification No. of patient, patient's consent, birth date or age, sex, pregnant or lactating status(in case of women), race, reason for use, initial (or scheduled) day of administration, administration status, examination category, contraindication items, careful administration, presence or absence of prior medications for ulcerative colitis and their effects, use history of biological products, tuberculosis and infection tests (tuberculin skin test, Quanti-Feron®

test, chest X-ray test, and CT test), HB virus tests (HBs antigen, HBs antibody, and HBc antibody), preventive administration of anti-tuberculosis agents, and clinical laboratory test values (β-D-glucan, peripheral WBC count, and peripheral lymphocyte count) before administration should be recorded.

(3) CRF

1) Patient information

height, body weight, smoking history, pathological condition of ulcerative colitis, disease duration, complication, past history, and allergy history

- 2) Ulcerative colitis-affected site
- Treatment history of ulcerative colitis with anti-TNFα
 Presence or absence of prior treatment with anti-TNFα, administration history, and reason for discontinuation
- 4) Prior medications or therapy for ulcerative colitis (within 3 months before administration of this drug)

History and type of prior medications or therapy

5) Administration status of this drug

Initial administration: Category of administration method, initial dose, and first

administration day

2nd administration: Category of administration method, 2nd dose, and day of 2nd

administration

3rd and subsequent administrations: Category of administration method, daily dose,

administration frequency, administration period, and reasons for

change to the dose and administration frequency

Self-injection: Presence or absence of consent to initiation of self-injection and

record on initiation of self-injection

Malpractice of self-injection: Y/N, onset day, and type/reason

6) Discontinuation of survey

Reason for discontinuation

7) Administration status of anti-tuberculosis agents

Presence or absence of administration of anti-tuberculosis agents, product name, daily dose, and administration period

8) Administration status of concomitant drug(s)

Concomitant drug for ulcerative colitis: drug name, reason for use, administration route, dose, and administration period

- 9) Other concomitant drugs: drug name, reason for use, administration route, dose, and administration period
- 10) Drugs/combination therapies other than medication for ulcerative colitis

Presence or absence of drugs/combination therapies other than medication for ulcerative colitis, name of therapy, and therapeutic duration

11) Presence or absence of onset of tuberculosis or serious respiratory disorders

Examination day, imaging diagnostic method, abnormal findings, and abnormality

12) Mayo Score

Examination day (at initiation of administration, week 4, 8, 16, 24, 32, and 52 of administration, and discontinuation of administration)

13) CRP

Examination day (at initiation of administration, week 4, 8, 16, 24, 32, and 52 of administration, and discontinuation of administration)

14) Endoscopic finding

Examination day (at initiation of administration, week 24, 52 of administration, and discontinuation of administration)

15) Overall improvement (judgment by attending physician)

Judgment day (at week 52 of administration or at discontinuation)

Overall improvement (Remarkably effective, Effective, Ineffective, and Unevaluable)

16) Adverse events (including abnormal change in laboratory values)

Occurrence of adverse events, name of adverse events, onset day, seriousness, causal relationship to this drug, suspected drug(s), symptom and clinical course, treatment (with this drug or symptomatic treatment), outcome, laboratory values (if abnormally changed), and judgment reason if no causality

17) Key survey items

Infection, tuberculosis, malignant tumor, administration site reaction, autoimmune disease, pancytopenia, demyelinating disorders, congestive cardiac failure, and interstitial pneumonia

18) Measurement of anti-adalimumab antibody

If measurement of anti-adalimumab antibody is judged to be necessary

9. Analysis and Methods

- (1) Analytical items
 - 1) Patient population
 - 1. No. of enrolled patients
 - 2. No. of CRFs recovered
 - 3. Safety evaluation set
 - 4. Efficacy evaluation set
 - 2) Safety
 - 1. List of adverse reactions and infections
 - 2. Factors likely to affect the safety

- Incidence of adverse reactions by patient background
- Presence or absence of the use experience with anti-TNFα preparation and the relationship of safety.
- Safety in Long-Term administration
- Relationship of safety when anti-adalimumab antibody was determined
- Safety in patients conducting self-administration
- 3. Adverse events which developed during or after administration
 - List of serious adverse events
 - Status of onset of intestinal infections including cytomegalovirus colitis, etc.
- 4. Main adverse events (infections including tuberculosis, malignant tumor, injection site reaction, allergic reaction, demyelinating disease, lupus-like syndrome, blood disorder) for which attention is called in the sections of warning, careful administration and important basic precautions in the package insert of the study drug
- 5. Onset of self-injection malpractice
- 6. Safety in pediatric UC patients

3) Efficacy

- Change in efficacy (Mayo score, Partial Mayo score etc.) by Week 52 of administration
- Presence or absence of the use experience with anti-TNF α preparation and the relationship of efficacy.
- Efficacy by the history of previous treatment
- Efficacy (including the incidence of secondary ineffectiveness) in long-term administration
 - Relationship between efficacy and safety when anti-adalimumab antibody was determined
 - Efficacy in pediatric UC patients
- 4) Patients with special background

List of adverse reactions and infections in patients with special background such as children, elderly, pregnancy, renal dysfunction, and hepatic dysfunction

(2) Analytical methods

Appropriate methods such as χ^2 test will be used, depending on the scale and property of the analytical data.

10. Action to be taken when use in pregnant woman was found

The effects on parturition and newborn are followed up as much as possible, if use in pregnant women was found.

11. Organization of Surveillance

This follows the master plan for post-marketing surveillance. The trustee appears in "12. Name

and Address of Person Who Was Entrusted with This Duty and Scope of the Duty" below.

12. Name and Address of Person Who Was Entrusted with This Duty and Scope of the Duty

(1) Trustee 1

2) Scope of duty

Implementation of "Specified Long-Term Use-Results Surveillance" (Asking the center or department for implementation of surveillance, contract, recovery of enrollment form and reinvestigation, recovery of CRF and reinvestigation, progress report of duty, and collection of information on adverse events (including abnormal change in laboratory values))

(2) Trustee 2

2) Scope of duty

The implementation of special use-results survey (patient enrollment activities, reporting the progress of activities, data management activities, statistical analysis activities, etc.)

13. Others

(1) Revision of protocol

The protocol is revised as needed after considering whether the revision of protocol is necessary or not, based on the new findings obtained as the surveillance advances. Similarly, the protocol is revised as needed after considering whether the revision of protocol is necessary or not, if a partial change application for dosage and administration or indications was approved during the reexamination period (excluding if a new reexamination period is designated).

(2) Measures to be taken for any problems or questions

When an unknown serious adverse event was suggested to develop, the incidence of adverse reactions extensively increased, some questions about the efficacy and safety were raised in comparison with clinical studies, or an alien adverse reaction was suggested to develop, "Specified Use-Results Surveillance" or "Post-marketing Clinical Study" is considered to be implemented to detect or validate their factors or to confirm the estimation results.

14. Amendments and Updates

Number	Date	Section of study Protocol	Amendment	Reason
Nullibel	Date		or Update	Reason

1	23 Feb 2016	6.4 Adverse Event	Amendment	FDA requirement
		Reporting		

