5.2. Analysis method

Appropriate tests including χ^2 test are employed for analysis, depending on the analysis-data scale and the characteristics.

6. Presence/absence of analysis and its schedule

Analysis objective	The survey's reporting interval and the deadline	
	of re-examination	
The 6th periodical safety	January 1, 2016 to December 31, 2016	
report		
Re-examination	June 14, 2013 to May 15, 2017	
Final report	June 14, 2013 to March 31, 2018	

7. Softwares/dictionary used for analysis

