7.2. Dictionary for use

The dictionaries used for the names of adverse events, complications, and drugs are as follows:

Item	Dictionary and its version	Remarks
Types of adverse events	Medical Dictionary for Regulatory	They are classified into a
and adverse	Activities / Japanese edition	System Organ Class (SOC) and
reactions/infections	(MedDRA/J 20.1)	the appropriate term among the
		preferred terms (PT) is selected
		for description.
		SOC is displayed in accordance
		with the international
		agreement.
		The MedDRA/J version used
		will be provided in a blank
		space.
Drug name (concomitant	Iyakuhinmei Data File (IDF) *An	• A 7-digit code is used, in
medication)	appropriate version should be used	principle, when concomitant
	for aggregation, depending on the	medications are counted per
	analysis period.	product.
		Give a priority to the lowest
		level codes when using codes
		for the list of concomitant
		medications (including
		Re-examination Attachment
		Form 3).

8. The definition of the groups used for analysis

Name of group	Definition
Registered patients	The patients assessed as eligible for registration
Patients whose survey	Registered patients whose survey form was locked.
form was locked	
Patients whose survey	Registered patients whose survey form was yet to be locked. See
form was yet to be	Reference Data "Survey form lock/unlock information" for the criteria
locked	for the status that a survey form is yet to be locked.
Patients excluded from	The patients whose survey form has been locked and who satisfy the
the safety analysis group	criteria of the patients excluded from the safety analysis group. See
	Reference Data "Inclusion/exclusion of patients" for the criteria to
	exclude patients from the safety analysis group.
	The exclusion items are as follows:
	Breach of contract: unsigned institutions/specialties
	Breach of contract: an excess of contracted number of patients
	Breach of contract: unsigned physicians
	Not treated with Humira
	Not confirmed by physician
	Overlapped patients
	Safety is not assessable
	Breach of registration criteria: a deviation from the registration period
	Breach of registration criteria: with a history of treatment with
	Humira
	Administration prior to contract
	Data credibility cannot be confirmed: closure/merger of medical
	institutions
	Data credibility cannot be confirmed: the physician was transferred
	Data credibility cannot be confirmed: the physician refuses
	confirmation

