Note: Follow the definition in "the reason for the change in dose/dosing frequency" of "10.1 General" for the reason for the change in dose/dosing frequency.

"1.6 Administration status of Humira (dosing frequency, dose)

Patients for analysis: patients in the safety analysis group, patients in the effectiveness analysis group

Analysis objective: to show the dosing frequency and the distribution status of the total dose

Analysis items: calculate the number of patients per segment defined in "11 How to stratify data" as well as the percentage to the number of patients in the analysis groups regarding dosing frequency and the total dose. In addition, calculate summary statistics for each measurement.

"1.6.1 Administration status of Humira (period)"

Patients for analysis: patients in the safety analysis group, patients in the effectiveness analysis group

Analysis objective: to show the distribution status in the administration period.

Analysis item: Calculate the administration dates based on "days to the final administration date of Humira" of "10.1 General" as well as the number of patients in the analysis groups. Then, calculate the number of patients per segment which contains the administrations date in each patient and the percentage to the patients in the analysis group in the Time Allowance defined in "12.1 Assessment period for administration status of Humira" In addition, calculate summary statistics for the number of days for administration.

"1.6.2 Continuation rate of Humira"

Patients for analysis: patients in the safety analysis group

Analysis objective: to show the continuation rate of Humira using the Kaplan-Meier method.

Analysis items: At Risk, number of discontinued patients, continuation rate (the percentage to the number of discontinued patients for At Risk), 95% of continuation rate

Calculate the confidence interval by assessment period. In addition, generate the Kaplan-Meier curve for the continuation rate.

Note: Follow "12.7 Assessment period for the continuation of Humira administration" for the dates of assessment period.

The days are censored at the first administration date of Humira + 364 in patients who are still registered at Week 52.

Calculate the analysis items using the Kaplan-Meier method.

At Risk should include the number of patients who are exposed to a discontinuation risk.

"1.7 Administration status of Humira (discontinuation of administration)"

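### At the 6th periodic and re-examination cut-offs, recently started patients can normally enter the locked-form analysis groups only if their surveillance was discontinued, which biases the interim continuation rate downward

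*Protocol*

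**What the plan says.** **When a form arrives.** Protocol 6(3), item 5 sets the normal rule: "A physician in charge completes CRF with the observation results at week 52 after initiation of administration, and submits the CRF to MR". The exception follows in the same item: "In cases of the observation period uncompleted, CRF is completed promptly when the surveillance was discontinued, and submitted to MR". Protocol 8(1) repeats that for a patient who stays on treatment "the CRF should be completed at the time point of week 52". It also handles a patient lost to follow-up through a move to another hospital as a discontinued case.

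**Who is analysed.** SAP 8 defines the starting set as "Registered patients whose survey form was locked". The safety analysis group is that set less exclusions, and the effectiveness group is a subset of the safety group. SAP 10.2 uses the safety group as the denominator for incidences.

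**When.** Protocol 7 gives "Surveillance period: July 2013 to March 2018 Enrollment period: July 2013 to July 2016", and lets both periods be shortened once the target is reached. SAP 6 lists a 6th periodic report to 31 December 2016, a re-examination analysis covering "June 14, 2013 to May 15, 2017", and a final report to 31 March 2018. The notes to Table 2.1 in SAP 13.2 list the same three.

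**Continuation rate.** Table 1.6.2 is meant "to show the continuation rate of Humira using the Kaplan-Meier method" in the safety group. Its only censoring rule is at first administration + 364 days, for patients still registered at Week 52.

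**The concern.** A discontinued patient's form can be locked soon after discontinuation. The form of a patient who started on the same day and continues cannot exist until Week 52. At a cut-off inside that window, inclusion therefore depends on the outcome being measured.

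Kaplan-Meier would cope with short follow-up if continuing patients entered as censored. Here they are outside the analysis group and contribute nothing. Nothing in the SAP requires 52 weeks of potential follow-up. SAP 3.1 names the re-examination application as one use of the plan, so what is at stake is the continuation rate, the discontinuation proportion and the related effectiveness rates in two interim regulatory outputs.

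**Working it through.** **Inputs from the documents.** 1500 patients and 70% dropout at Week 52 (Protocol 2); enrolment July 2013 to July 2016 (Protocol 7), taken as 1 July 2013 to 31 July 2016, a span of 1127 days; cut-offs from SAP 6.

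**The plan's own figure.** 1500 × 0.30 = 450 patients at Week 52; 450 × 0.70 = 315 with a Mayo score; 1.96 × √(0.3 × 0.7 / 315) = 5.06%, giving 24.9 to 35.1. Table 1 of Protocol 2 reproduces. The documents give no figure for the make-up of the locked set at an interim cut-off.

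**Dates.** With the first dose as Day 1, Day 365 falls on or before the cut-off only for starts up to 2 January 2016 (6th report) or 16 May 2016 (re-examination). A patient who started on 31 July 2016 reaches Day 365 on 30 July 2017, about eight months before 31 March 2018.

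**Assumptions not in the documents.** Uniform enrolment; first dose at enrolment; dropout at a constant hazard, with every dropout also ending the surveillance; form available at the earlier of stopping and Week 52, plus a lock time g that is the same for all. I take g = 0 and g = 182 days. The true 70% is varied to 50% and 30%.

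**Formulas.** A = days from 1 July 2013 to the cut-off: 1279 (6th report) and 1414 (re-examination). d = dropout; λ = −ln(1 − d)/364, which is 0.003308 per day at d = 0.70.

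- Mature patients: M = 1500 × (A − g − 364)/1127.
- Shortest usable follow-up among the others: f = max(0, A − g − 1127).
- Discontinued patients with a locked form among those not mature: E = (1500/1127) × [(364 − f) − (e^(−λf) − (1 − d))/λ].
- Locked set = M + E. Nobody in it is censored before Day 364, so Kaplan-Meier at Week 52 equals the plain proportion (1 − d)M/(M + E).

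Example, 6th report, g = 0, d = 0.70: M = 1500 × 915/1127 = 1218; f = 152; E = 1.331 × [212 − (0.605 − 0.300)/0.003308] ≈ 160; continuation = 0.3 × 1218/(1218 + 160) = 26.5%.

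| Cut-off, lock time | M | E (d = 0.70) | Continuation, true 30% | True 50% | True 70% |
|---|---|---|---|---|---|
| 6th report, 0 days | 1218 | 160 | 26.5% | 45.9% | 66.6% |
| 6th report, 182 days | 976 | 203 | 24.8% | 43.9% | 64.9% |
| Re-examination, 0 days | 1398 | 68 | 28.6% | 48.4% | 68.6% |
| Re-examination, 182 days | 1155 | 181 | 25.9% | 45.2% | 66.0% |
| Final report, either | 1500 | 0 | 30.0% | 50.0% | 70.0% |

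At 30% or 70% dropout the shortfall is 3.4 to 5.2 points at the 6th report and 1.4 to 4.1 at re-examination. At 50% dropout it reaches about 6 and 5 points. Replacing the exponential by a linear or front-loaded dropout curve, at 70% dropout, gives about 24 to 27% and 26 to 29% against a true 30%. The sampling 95% half-width at these set sizes is about 2.3 to 2.9 points, so the printed interval would not reveal a shift of this kind.

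**Which other tables move.** Tables 3.2 and 3.4 take a discontinued patient's judgement at discontinuation (SAP 12.5). Table 3.4.1 uses the final assessment (SAP 12.4). The NRI results (3.1.5.2 and the NRI versions of 3.1.7.1 and 3.1.7.2) count an unknown Week 52 status as no remission. All should shift toward failure where discontinuation reflects failure, but the documents offer nothing from which to size this.

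**The case against.** **The interim analyses look historical.** SAP version 2.1 is dated 12 March 2018, after both cut-offs, and version 2.0 renamed files for the final report. This stands as a limit on urgency. It does not remove the point, because SAP 6 and the Table 2.1 notes still list both analyses.

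**The trigger is the end of surveillance.** A reader might infer that every recently started patient in the set has stopped Humira. The text does not say so. A patient who stops the drug but is observed to Week 52 has no early form, and a patient who changes hospital while on Humira has one. The link is indirect: SAP 10.1 classifies discontinuation by last dose but takes reasons from the survey-discontinuation item.

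**Lock criteria are not shown.** SAP 8 refers them to a separate reference file. Lock time is therefore assumed, and it drives most of the re-examination effect.

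**The effect is modest and conditional.** With no lock time the re-examination shift is 1.4 points at 70% dropout. Had enrolment closed by 16 May 2016, it would be nil at re-examination; by 2 January 2016, nil at both cut-offs. Actual accrual is not in the documents.

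**Not every table is affected.** It is tempting to extend the point to all effectiveness tables. The observed-case Week 52 results (3.1.1, 3.1.2, 3.1.4, 3.1.5.1) need an assessment on Days 337 to 393, so early forms contribute almost nothing there. Nor is there an argued case for removing patients from the safety factor table (2.9).

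**Partly disclosed.** Tables 1.1 and 1.3.1 report forms not yet locked. They show incompleteness but do not say that the missing patients are mainly continuers, and they correct no rate. Events added from the adverse-event matching results can change numerators only.

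**Conclusion.** The mechanism and its direction follow from the documents. If enrolment ran to July 2016, the 6th periodic and re-examination analyses select recent starters on discontinuation, and Tables 1.6.2 and 1.7 are biased toward it. Under the stated model, Week 52 continuation is understated by about 3 to 5 points at the 6th report and 1 to 4 points at re-examination at 30% or 70% dropout, and by slightly more at 50%. The effectiveness tables named above probably shift toward failure, by an unknown amount.

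A reader might conclude that the survey's final rates are also distorted. They are not: at 31 March 2018 every planned patient has passed Week 52, with about eight months left for locking. The point is a limited correction to two interim outputs, conditional on actual accrual and lock time.

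**What to change.** In SAP 6 and 8, add one sentence for the 6th periodic and re-examination analyses. Tables 1.6.2, 1.7, 3.2, 3.4, 3.4.1 and any NRI table run at those cut-offs should use only patients whose first administration was at least 52 weeks plus the usual lock time before the cut-off, whether they discontinued or continued. State the lock time used. Under the equal-lock-time model this restores the true continuation rate.

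Leave the safety tables (including 2.9), the listings and the Attachment Form counts on all locked forms, with later starters marked as not yet mature, so that no safety case is lost.

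If these analyses have already been run, either re-run the listed tables with the filter, or state the limitation and rely on the final report for these rates.

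Cost: a date filter on a field already collected. Across 30% to 70% dropout, about 28 patients (re-examination, no lock time, 30%) to 203 patients (6th report, six months, 70%) with early discontinuation leave the interim rate tables. The final report does not change.
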